3.0 OBJECTIVE(S) & HYPOTHESIS(ES)

3.1 Primary Objective(s) & Hypothesis(es)

(1) **Objective:** To evaluate the safety, tolerability, and to determine the maximum tolerated dose (MTD) of vorinostat given in combination with pembrolizumab, temozolomide, and radiotherapy in patients with newly diagnosed glioblastoma.

Hypothesis: Combination of pembrolizumab and vorinostat with radiotherapy and temozolomide will have acceptable safety and tolerability.

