Vorinostat will be administered orally at 100, 200 or 300 mg/day dose on days 1-5 every week (based on dose level); starting on first day of radiotherapy. Safety and tolerability of vorinostat 300 mg/day dose on days 1-5 every week in combination with temozolomide (75 mg/m²/day orally) has been proven in a phase I/II trial (N0874-ABTC 0902, Alliance) by Galanis et al. 2014 [38].

Pembrolizumab will be administered as an IV intravenous infusion and will be evaluated at 200 mg. Pembrolizumab will be administered every 3 weeks (+/-3 days) starting on first day (+/- 3 days) of radiotherapy.

Table 2 summarizes the doses for pembrolizumab and vorinostat during radiotherapy part of treatment.

	Dose Escalation Schedule During Radiotherapy Phase				
Dose Level		Dose			
	Pembrolizumab	Vorinostat			
Level -1	200 mg IV every 3 weeks	100 mg/day orally on days 1-5 every week during radiotherapy			
Level 1	200 mg IV every 3 weeks	200 mg/day orally on days 1-5 every week during radiotherapy			
Level 2	200 mg IV every 3 weeks	300 mg/day orally on days 1-5 every week during radiotherapy			

Maintenance Phase:

During maintenance phase, temozolomide will start 4 weeks (+/- 7 days) after last dose of radiotherapy and will continue for 6 cycles post radiotherapy (150-200 mg/m²/day, days 1-5 every 4 +/- 1 weeks) as per standard of care [22]. As per standard of care, the starting dose for the first cycle will be 150 mg/m²/day, with a single dose escalation to 200 mg/m²/day in subsequent cycles if no temozolomide-related adverse events > Grade 2 are noted. The dose will be determined using the BSA calculated at the beginning of each treatment cycle. The BSA will be calculated from the height obtained at the screening visit and from the weight obtained at the visit immediately before each cycle. The dose of temozolomide does not have to be adjusted unless there has been at least a 10% change in body weight; recalculation of dose for < 10% weight changes is allowed at the discretion of the Investigator. The dose will also not be capped for those that are overweight. The daily dose will be rounded to the nearest 5 mg (where dosage strengths are available to accommodate rounding to 5 mg).

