Vorinostat will be administered orally at 200, 300 or 400 mg/day (based on dose level) on a 1 week on 1 week off schedule for 12 months. Vorinostat will start the day after completion of radiotherapy (+ 3 days). Safety of vorinostat 400 mg/day on a 1 week on 1 week off schedule in combination with maintenance temozolomide has been shown in a phase 1 study by Lee et al. 2012 [34].

Pembrolizumab 200 mg IV will continue every 3 weeks (+/-3 days) for 12 months or 18 infusions whatever comes first

Table 3 summarizes the doses for pembrolizumab and vorinostat during maintenance part of treatment.

Table 3 Dose Escalation Schedule for Pembrolizumab and Vorinostat maintenance part of treatment.

	Dose Escalation Schedule During Maintenance Phase					
Dose Level	Dose					
	Pembrolizumab	Vorinostat				
Level -1	200 mg IV every 3 weeks	200 mg/day orally 1 week on 1 week off after radiotherapy				
Level 1	200 mg IV every 3 weeks	300 mg/day orally 1 week on 1 week off after radiotherapy				
Level 2	200 mg IV every 3 weeks	400 mg/day orally 1 week on 1 week off after radiotherapy				

In all patients, treatment with study drugs will continue until confirmed disease progression, patient refusal, patient lost to follow up, unacceptable toxicity, completion of scheduled dosing, whichever occurs first, or the study is terminated by the Sponsor (Moffitt Cancer Center).

Dose Expansion Phase:

The vorinostat doses used in the dose expansion cohort will be MTD determined from the dose escalation phase.

Definition of Maximum Tolerated Dose:

The maximum tolerated dose (MTD) is the highest dose of vorinostat in combination with pembrolizumab, temozolomide during and after radiation therapy that does not cause unacceptable toxicity in more than one of six patients at that dose level. The MTD is defined as one dose level below the highest toxic dose (i.e., the DLT dose).

Details on preparation and administration of pembrolizumab (MK-3475) are provided in the Pharmacy Manual.

5.3.1 5.3.1 Definition of Dose-Limiting Toxicity

Toxicities will be graded in severity according to the guidelines outlined in the NCI-CTCAE version 4.0. Dose limiting CNS and non-CNS toxicities will be defined differently and will be based on events that occur during the study period. In order to be declared as dose-limiting toxicity, an adverse event must be related to pembrolizumab and/or vorinostat.

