A dose-limiting toxicity (DLT) will be defined as any one of the following adverse events occurring within 6 weeks from last dose of radiation therapy for radiotherapy phase and 4 weeks from the start day of maintenance dose of vorinostat [Cycle 1 Day 43 (+/-3)] for maintenance phase:

CNS toxicities:

Acute CNS toxicities (occurring \leq 30 days after completing radiation therapy):

 Any grade 3 or higher central nervous adverse events including but not limited to headache, dizziness, vertigo, new onset seizures, cerebral edema, cerebral hemorrhage, and new onset neurologic deficit.

Delayed onset CNS toxicities (occurring >30 days after completing radiation therapy):

• Any grade 3 or 4 adverse event arising within the irradiated volume including but not limited to focal neurological deficits.

Non-CNS toxicities:

- Any Grade 4 immune-related adverse event (irAE)
- Any \geq Grade 3 colitis
- Any Grade 3 or 4 non-infectious pneumonitis irrespective of duration
- Any Grade 2 pneumonitis that does not resolve to ≤ Grade 1 within 3 days of the initiation of maximal supportive care
- Any Grade 3 irAE, excluding colitis or pneumonitis, that does not downgrade to Grade 2 within 3 days after onset of the event despite optimal medical management including systemic corticosteroids or does not downgrade to ≤ Grade 1 or baseline within 14 days
- Liver transaminase elevation > 8 × upper limit of normal (ULN) or total bilirubin > 5 × ULN
- Any \geq Grade 3 non-irAE, except for the exclusions listed below

The definition excludes the following conditions:

- Grade 3 fatigue lasting ≤ 7 days
- Grade 3 endocrine disorder (thyroid, pituitary, and/or adrenal insufficiency) that is managed with or without systemic corticosteroid therapy and/or hormone replacement therapy and the subject is asymptomatic
- Grade 3 inflammatory reaction attributed to a local antitumor response (eg, inflammatory reaction)
- Concurrent vitiligo or alopecia of any AE grade

- Grade 3 infusion-related reaction (first occurrence and in the absence of steroid prophylaxis) that resolves within 6 hours with appropriate clinical management
- Grade 3 or 4 neutropenia that is not associated with fever or systemic infection that improves by at least 1 grade within 14 days. Grade 3 or Grade 4 febrile neutropenia will be a DLT regardless of duration or reversibility
- Grade 3 or 4 lymphopenia

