6.0 TRIAL FLOW CHART

6.1 Study Flow Chart

Concurrent Radiotherapy Phase

Trial Period:	Screeni	ng Phase						Tr	eatmen	t Cycle	es			
Treatment Cycle/Title:	Pre- screening (Visit 1)	Main Study Screening (Visit 2) ^a	Cycle 1 (Concurrent therapy with radiation, 12 weeks)											
Scheduling Window (Days):		-21 to -1	D1 ± 3	D8 ± 3	D15 ± 3	D22 ± 3	D29 ± 3	D36 ± 3	D43 ± 3	D50 ± 3	D57 ± 3	D64 ± 3	D71 ± 7	D78 ± 3
Administrative Procedures									ı					
Informed Consent	X													
Inclusion/Exclusion Criteria		X												
Demographics and Medical History	X	X	X			X			X			X		
Prior and Concomitant Medication Review	X	X	X			X			X			X		
Radiation therapy				(Total c	lose of (X 60 Gy; 1	Monday	-Friday	·)					
Temozolomide					F	X Every da	ıy						X (5 day regimen every 28 days)	
Pembrolizumab			X			X			X			X		
Vorinostat				l	Dail	y one v	-		-	ek duri starting	-		+/- 3 days	
Post-study anticancer therapy status														
Survival Status														
Clinical Procedures/Assessments														
Review Adverse Events ^c			X			X			X			X		
Full Physical Examination	X	X	X			X			X			X		

Trial Period:	Screeni	Treatment Cycles												
Treatment Cycle/Title:	Pre- screening (Visit 1)	Main Study Screening (Visit 2) a	Cycle 1 (Concurrent therapy with radiation, 12 weeks)											
Scheduling Window (Days):		-21 to -1	D1 ± 3	D8 ± 3	D15 ± 3	D22 ± 3	D29 ± 3	D36 ± 3	D43 ± 3	D50 ± 3	D57 ± 3	D64 ± 3	D71 ± 7	D78 ± 3
Vital Signs and Weight	X	X	X			X			X			X		
EORTC QLQ-C30 and BNS20 Questionnaire			X			X			X			X		
Karnofsky Performance Status	X	X	X			X			X			X		
Laboratory Procedures/Assessments: analy	sis perform	ed by LOCA	L labor	ratory										
Pregnancy Test – Urine or Serum β-HCG		X												
PT/INR and aPTT		X												
CBC with Differential	X	X	X	X	X	X	X	X	X	X	X	X	X	X
Comprehensive Serum Chemistry Panel	X	X	X			X			X			X		
Urinalysis	X	X	X			X			X			X	X	
T3, FT4 and TSH	X	X	X			X			X			X		
Efficacy Measurements														
Brain MRI with/without contrast		X											X	
Tumor Biopsies/Archival Tissue Collection	/Correlative	e Studies Bloo	od											
Archival or Newly Obtained Tissue Collection		X												
Correlative Studies Blood Collection			X			X			X					

^a Visit 1 assessment (physical examination and laboratories) can be used for main study screening (visit 2) if visit 2 occurs within 3 days from visit 1.

^b There will be two follow up visits which include full physical examination, laboratories, and brain MRI.

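### The maintenance DLT window closes about when maintenance temozolomide starts, and it lies inside the radiotherapy-phase window with no rule for which dose level an event counts against

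*Combined protocol and SAP*

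**What the plan says.** **Maintenance DLT window.** Section 5.3.1 gives "4 weeks from the start day of maintenance dose of vorinostat [Cycle 1 Day 43 (+/-3)] for maintenance phase". The same section uses the same 4 weeks as the hold before maintenance expansion, so the length is not a one-off slip.

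**Radiotherapy-phase DLT window.** Section 5.3.1 ends it 6 weeks after the last radiation dose. It does not say when the window opens.

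**Start of the maintenance drugs.** Section 5.3 (Maintenance Phase) starts vorinostat the day after radiotherapy, with up to 3 days' grace, "on a 1 week on 1 week off schedule for 12 months". For temozolomide it says "During maintenance phase, temozolomide will start 4 weeks (+/- 7 days) after last dose of radiotherapy", then "days 1-5 every 4 +/- 1 weeks". The flow chart (Section 6.1) first shows the 5-day temozolomide regimen under Day 71 ± 7.

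**What the MTD refers to.** The primary objective (Section 3.1) is "to determine the maximum tolerated dose (MTD) of vorinostat given in combination with pembrolizumab, temozolomide, and radiotherapy". The MTD definition in Section 5.3 is for vorinostat "in combination with pembrolizumab, temozolomide during and after radiation therapy".

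**Counting.** Sections 2.1 and 5.3 escalate the two phases separately. Section 5.3.1 counts DLTs by patient and requires a relation to pembrolizumab and/or vorinostat. Both drugs are given in both phases. No section says which phase's level is charged when an event meets both window definitions.

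**The concern.** There are two linked problems.

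First, the maintenance MTD is to be stated for a combination that its observation window scarcely covers. Toxicity arising from maintenance vorinostat and pembrolizumab together with maintenance-dose temozolomide would mostly appear after the window has closed.

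Second, the two windows overlap while the two escalations are meant to be separate. In a 3+3 design one or two events decide a level, so an event charged to both levels, or to the level of the phase that has already ended, can change the decision. Section 5.3 reports that the radiotherapy-phase level has already been reduced for DLT and the maintenance level escalated, so the missing rule bears on decisions already taken.

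**Working it through.** **Notation.** R = day of the last fraction; V = first day of maintenance vorinostat; T = first day of maintenance temozolomide. Figures leave out the window's closing day, V+28; figures in square brackets count it.

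**1. The plan's own anchor.** Thirty weekday fractions (Sections 5.2.1 and 5.3) from Day 1 end on Day 40 for a Monday start and on Day 42 otherwise. V = R+1 to R+4 is then Days 41–44 or 43–46. Day 43 lies in both, so the bracketed Day 43 is reproduced, and 43 + 28 = Day 71.

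**2. Overlap with maintenance temozolomide.** Overlap = max(0, V + 28 − T), plus 1 if the closing day counts and T ≤ V + 28.

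| | Section 5.3 text | Day 43 ± 3 with flow chart |
|---|---|---|
| V | R+1 to R+4 | Days 40–46 |
| T | R+21 to R+35 | Days 64–78 |
| Date pairs | 4 × 15 = 60 | 7 × 15 = 105 |
| Nominal overlap, days | 29 − 28 = 1 [2] | 71 − 71 = 0 [1] |
| Maximum overlap, days | 32 − 21 = 11 [12] | 74 − 64 = 10 [11] |
| Pairs with the whole 5-day course inside | 22 [26] | 21 [28] |
| Pairs with no temozolomide day inside | 22 [18] | 56 [49] |
| Pairs with a 21-day cycle inside | 0 [0] | 0 [0] |

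Mixing the two sets (V = Day 46, T = 40 + 21 = Day 61) gives 74 − 61 = 13 [14] days. These are counts of permitted dates, not probabilities.

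Sensitivity: adding the ± 3 days of Section 5.3.3 to both starts (V = R−2 to R+7, T = R+18 to R+38) still gives 0 of 210 pairs, with at most 17 [18] cycle days inside. A 21-day cycle fits only if radiotherapy starts 3 days before cycle Day 1 (R = Day 37), vorinostat starts on Days 47–49 and temozolomide starts before its own window. Those vorinostat dates breach the R+1 to R+4 rule. A 28-day cycle never fits.

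**3. Nesting.** By the text the latest close is R+32, before R+42. By the flow chart it is Day 74, before Day 82. The maintenance window therefore closes inside the radiotherapy-phase window in every pair. R+42 is Day 82 or 84, so 82 − 71 = 11 or 84 − 71 = 13 days follow a Day 71 close.

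**4. Literal counting.**
- Event from V to V+28: both levels.
- Event after V+28 and up to R+42: radiotherapy level only.
- Event after R+42: neither level.

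At nominal dates the vorinostat weeks are Days 43–49, 57–63 and 71–77, and temozolomide is Days 71–75. The first week with both drugs is Days 71–77, and at least six of its seven days fall in the radiotherapy-only interval.

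**5. Illustration only.** The documents give no DLT risks, so these are assumed, and the grade 2 CNS trigger in the decision table is left out. With p the DLT risk and q = 1 − p, a level clears 3+3 with probability q³ + 3pq²·q³.
- p = 0.10 inside the window: 0.729 + 0.177 = 0.906.
- If the risk through one temozolomide cycle were 0.15, 0.20 or 0.30: 0.814, 0.709 or 0.494.
- Radiotherapy level at 0.10 with an independent 0.10 or 0.20 added from maintenance: p = 1 − 0.9 × 0.9 = 0.19 or 1 − 0.9 × 0.8 = 0.28. The stop probability rises from 0.094 to 0.270 or 0.464.

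**The case against.** The strongest reply is the attribution rule. Temozolomide is background standard of care and is not escalated, and a toxicity due only to temozolomide can never be a DLT. The nominal window contains two full weeks of maintenance vorinostat with pembrolizumab, and nothing in the protocol requires a full temozolomide cycle inside it. This stands, and it limits the point to toxicity of the combination. It does not remove the point, because the MTD is defined for that combination.

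There are also safeguards. Expansion is meant to confirm safety (Section 8.1). Section 5.3.1 lets the sponsor and investigators add unlisted events as DLTs. Section 5.3.2.2.2 modifies vorinostat throughout treatment, and Sections 5.10 and 10.3 allow stopping. Section 5.3 cites earlier vorinostat–temozolomide experience, without pembrolizumab. An expansion patient starting on Day 71 of the last escalation patient reaches maintenance on about Day 71 + 42 = 113, after that patient's nominal first cycle ends (Day 99). The practical exposure gap is therefore smaller than the window alone suggests. None of this makes the window match the MTD definition or says how events are charged.

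Charging delayed CNS events to radiotherapy may be intended, but the text does not separate them from other events.

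A reader might infer that vorinostat and maintenance temozolomide can hardly ever be taken on the same day inside the window. That would need an exact 7-on/7-off calendar. The flow chart allows ± 3 days: with V = R+4 the second on-week, R+18 to R+24, may shift to R+21 to R+27 and then covers all five temozolomide days from R+21.

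**Conclusion.** The concern holds as a mismatch between the MTD definition and the window, together with a missing counting rule. It should be fixed before the maintenance MTD is declared. The overlap is 0–2 days nominally, at most 10–12 days within the stated start windows and 13–14 if they are mixed, and no cycle of 21 days or longer fits.

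The nesting assumes that the radiotherapy-phase window includes the treatment period, since the text gives only its end. The calendar days assume 30 uninterrupted weekday fractions. If radiotherapy takes 7 weeks, the bracketed Day 43 ± 3 itself conflicts with starting vorinostat after radiotherapy.

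Three stronger readings are not supported:
- That the window never observes maintenance temozolomide, or that a DLT in the first combined week always counts against radiotherapy only. Both fail at early temozolomide dates, when the whole 5-day course falls inside.
- That all later maintenance events go to the radiotherapy level. This ends 6 weeks after radiotherapy.
- That the level changes already made were wrong. The documents do not date or describe those DLTs, so they show only that a check is needed.

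The 3+3 probabilities show direction under assumed risks and are not estimates for this trial. Those for the radiotherapy level have limited forward relevance, because that level has already been reduced to the lowest listed and is being expanded.

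**What to change.** Reconcile the Maintenance Phase text and MTD definition in Section 5.3, the windows and hold in Section 5.3.1, and the temozolomide row in Section 6.1.

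1. **MTD statement.** At minimum, state in the MTD definition and in the conclusions that the maintenance MTD was established with little or no maintenance temozolomide exposure. This costs no delay, only a narrower conclusion. The sponsor may instead choose to align the window and hold with first-cycle exposure. For a 28-day cycle that adds 99 − 71 = 28 days per remaining maintenance cohort at nominal dates. At permitted dates it adds up to (35 + 28) − 29 = 34 days by the text or (78 + 28) − 68 = 38 days by the flow chart, about 5 weeks. Nominally, 11 to 13 of those days already fall inside the radiotherapy-phase window for the same patients. A longer window may also mean more replacements under the 85% rule in Section 5.9.
2. **Counting rule.** State when the radiotherapy-phase window opens. State how an event counts toward each level when it falls in both windows, or only in the later part of the radiotherapy-phase window. The choice is the sponsor's; the cost is a sentence or two.
3. **Re-check.** Apply that rule to the DLTs already counted, including those behind the level changes reported in Section 5.3.

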- Grade 3 or 4 thrombocytopenia that is not associated with clinically significant bleeding that requires medical intervention, and improves by at least 1 grade within 14 days
- Isolated Grade 3 electrolyte abnormalities that are not associated with clinical signs or symptoms and are reversed with appropriate maximal medical intervention within 3 days
- Immune-related AEs are defined as AEs of an immune nature (ie, inflammatory) in the absence of a clear alternative etiology. In the absence of a clinically significant abnormality, repeat laboratory testing will be conducted to confirm significant laboratory findings prior to designation as a DLT. Laboratory abnormalities that are not deemed to be clinical significant will not be considered a DLT.

While the rules for adjudicating DLTs in the context of dose exploration are specified above, an AE not listed above may be defined as a DLT after a consultation with the sponsor and investigators, based on the emerging safety profile.

Dose escalation will be determined based on the occurrence of DLTs. For the purposes of determining whether to advance the dose levels, DLTs will be counted by patient. For all observed toxicities, subjects should be assessed for inter-current illness or other causes and treated as appropriate.

In the event of the development of any grade 3 or 4 toxicity felt to be at least possibly related to pembrolizumab, pembrolizumab will be held until resolution to grade 1 or baseline assuming that occurs within 6 weeks window. Treatment with pembrolizumab can be resumed after resolution of DLT to grade 1 or baseline except for following adverse events: Grade 4 infusion reactions, \geq Grade 3 pneumonitis, \geq Grade 3 nephritis, \geq Grade 3 colitis, increased alanine aminotransferase (ALT) or aspartate aminotransferase (AST) greater than 5 times upper limit of normal or total bilirubin greater than 3 times upper limit of normal.

Dose escalation for vorinostat will follow the standard 3+3 design. The enrollment to expansion cohort for radiotherapy phase will be delayed for 6 weeks after the completion of radiation therapy by the last patient enrolled at the MTD dose level for radiation therapy phase. The enrollment to expansion cohort for maintenance phase will be delayed for 4 weeks after the start day of maintenance dose of vorinostat [Cycle 1 Day 43 (+/-3)] by the

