5.3.2.2.1 Pembrolizumab

Adverse events (both non-serious and serious) associated with pembrolizumab exposure may represent an immunologic etiology. These adverse events may occur shortly after the first

dose or several months after the last dose of treatment. Pembrolizumab must be withheld for drug-related toxicities and severe or life-threatening AEs as per Table 4 below.

See Section 5.6.1 and Events of Clinical Interest Guidance Document for supportive care guidelines, including use of corticosteroids.

Table 4 Dose Modification Guidelines for Pembrolizumab-Related Adverse Events

Toxicity	Hold Pembrolizumab For Grade	Timing for Restarting Pembrolizumab	Discontinue Subject
Diarrhea/Colitis	2-3	Toxicity resolves to Grade 0-1.	Toxicity does not resolve within 12 weeks of last dose or inability to reduce corticosteroid to 10 mg or less of prednisone or equivalent per day within 12 weeks.
	4	Permanently discontinue	Permanently discontinue
AST, ALT, or Increased	2	Toxicity resolves to Grade 0-1	Toxicity does not resolve within 12 weeks of last dose.
Bilirubin	3-4	Permanently discontinue (see exception below) ¹	Permanently discontinue
Type 1 diabetes mellitus (if new onset) or Hyperglycemia	T1DM or 3-4	Hold pembrolizumab for new onset Type 1 diabetes mellitus or Grade 3-4 hyperglycemia associated with evidence of beta cell failure.	Resume pembrolizumab when patients are clinically and metabolically stable.
Hypophysitis	2-3	Toxicity resolves to Grade 0-1	Toxicity does not resolve within 12 weeks of last dose or inability to reduce corticosteroid to 10 mg or less of prednisone or equivalent per day within 12 weeks.
	4	Permanently discontinue	Permanently discontinue
Hyperthyroidism	3	Toxicity resolves to Grade 0-1	Toxicity does not resolve within 12 weeks of last dose or inability to reduce corticosteroid to 10 mg or less of prednisone or equivalent per day within 12 weeks.
	4	Permanently discontinue	Permanently discontinue
Hypothyroidism	2-4	Therapy with pembrolizumab can be continued while treatment for the thyroid disorder is instituted	Therapy with pembrolizumab can be continued while treatment for the thyroid disorder is instituted.
Infusion Reaction	3-4	Permanently discontinue	Permanently discontinue

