Pneumonitis	2	Toxicity resolves to Grade 0-1 Permanently discontinue if recurrent pneumonitis.	Toxicity does not resolve within 12 weeks of last dose or inability to reduce corticosteroid to 10 mg or less of prednisone or equivalent per day within 12 weeks. Discontinue pembrolizumab permanently for recurrent Grade 2 pneumonitis.
	3-4	Permanently discontinue	Permanently discontinue
Renal Failure or Nephritis	2	Toxicity resolves to Grade 0-1	Toxicity does not resolve within 12 weeks of last dose or inability to reduce corticosteroid to 10 mg or less of prednisone or equivalent per day within 12 weeks.
	3-4	Permanently discontinue	Permanently discontinue
All Other Drug- Related Toxicity ²	3 or Severe	Toxicity resolves to Grade 0-1	Toxicity does not resolve within 12 weeks of last dose or inability to reduce corticosteroid to 10 mg or less of prednisone or equivalent per day within 12 weeks.
Tomotty	4	Permanently discontinue	Permanently discontinue

Note: Permanently discontinue for any severe or Grade 3 drug-related AE that recurs or any life-threatening event.

¹ For patients with liver metastasis who begin treatment with Grade 2 AST or ALT, if AST or ALT increases by greater than or equal to 50% relative to baseline and lasts for at least 1 week then patients should be discontinued.

² Patients with intolerable or persistent Grade 2 drug-related AE may hold study medication at physician discretion. Permanently discontinue study drug for persistent Grade 2 adverse reactions for which treatment with study drug has been held, that do not recover to Grade 0-1 within

Toxicity	Hold Pembrolizumab For Grade	Timing for Restarting Pembrolizumab	Discontinue Subject
12 weeks of the last dose.			

Dosing interruptions are permitted in the case of medical / surgical events or logistical reasons not related to study therapy (e.g., elective surgery, unrelated medical events, patient vacation, and/or holidays). Subjects should be placed back on study therapy within 3 weeks of the scheduled interruption, unless otherwise discussed with the Sponsor. The reason for interruption should be documented in the patient's study record.

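### Section 5.3.1 and Tables 4 and 5 give different rules for holding, resuming and stopping pembrolizumab, and no text says which governs

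*Combined protocol and SAP*

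**What the plan says.** Section 5.3.1, after defining DLTs, sets a hold for any Grade 3 or 4 toxicity thought possibly due to pembrolizumab: "pembrolizumab will be held until resolution to grade 1 or baseline assuming that occurs within 6 weeks window". It continues: "Treatment with pembrolizumab can be resumed after resolution of DLT to grade 1 or baseline except for following adverse events: Grade 4 infusion reactions". The other exceptions are pneumonitis, nephritis and colitis of Grade 3 or worse, and raised liver tests. In part, the list reads "Grade 3 colitis, increased alanine aminotransferase (ALT) or aspartate aminotransferase (AST) greater than 5 times upper limit of normal".

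Table 4 in Section 5.3.2.2.1 covers the same drug, event by event:

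- Colitis: "Diarrhea/Colitis 2-3 Toxicity resolves to Grade 0-1". Only Grade 4 is a permanent stop.
- Recovery limit in the hold-and-restart rows, apart from diabetes/hyperglycemia: "Toxicity does not resolve within 12 weeks of last dose".
- Infusion reactions: "Infusion Reaction 3-4 Permanently discontinue Permanently discontinue".
- Hypothyroidism, Grades 2 to 4: "Therapy with pembrolizumab can be continued while treatment for the thyroid disorder is instituted".
- General note: "Permanently discontinue for any severe or Grade 3 drug-related AE that recurs or any life-threatening event".

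Table 5 in Section 5.6.1 also ends dosing after a Grade 3 or 4 infusion reaction.

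**The concern.** These are two rules for the same decision, a few pages apart, and neither mentions the other. An investigator working from the DLT section could re-dose a patient after an event that Tables 4 and 5 treat as a permanent stop. The same investigator could end treatment in a patient with resolved Grade 3 colitis whom Table 4 would restart.

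The primary objective covers safety and tolerability as well as the MTD, in at most 32 patients. How many of them stop pembrolizumab for toxicity, and how much drug they receive, would then depend partly on which section was followed.

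**Working it through.** The main check sets the texts side by side. Arithmetic enters only for the time windows.

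**1. Reach of each sentence in Section 5.3.1.** The hold sentence, with its 6 weeks, applies to any related Grade 3 or 4 event. The resume sentence applies to DLTs only. By Section 5.3.1, DLTs arise within 6 weeks of the last radiation dose (radiotherapy phase) or 4 weeks of starting maintenance vorinostat (maintenance phase). Radiotherapy lasts 6 to 7 weeks (Section 5.2.1), so the first window closes 6 + 6 = 12 to 7 + 6 = 13 weeks after radiotherapy starts. The second closes earlier, nominally at Day 43 + 28 = Day 71. Later events fall outside the resume sentence.

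**2. Which events are DLTs.** Every related Grade 4 immune-related event is a DLT, and the endocrine exclusion covers Grade 3 only. Immune-related Grade 4 hypophysitis or hyperthyroidism inside the window is therefore a DLT, and neither is on the no-resume list. A Grade 3 infusion reaction is excluded only if it is a first episode, without prior steroid cover, and settles within 6 hours. Other related Grade 3 reactions can be DLTs, and the no-resume list names only Grade 4 reactions.

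**3. Comparison, for events attributed to pembrolizumab.**

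| Event | Section 5.3.1 | Tables 4 and 5 | 5.3.1 is |
|---|---|---|---|
| Grade 3 colitis (DLT) | No resumption | Restart at Grade 0-1 | Stricter |
| Grade 3 infusion reaction that is a DLT | May resume | Permanent stop | Looser |
| Unlisted Grade 4 DLT, e.g. hypophysitis, hyperthyroidism | May resume | Permanent stop | Looser |
| Recovery time, any related Grade 3-4 event | 6 weeks, no start point, no stated consequence | 12 weeks from last dose | Shorter |
| Grade 3-4 hypothyroidism | Hold | Row lets dosing continue | Stricter |

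The two texts agree on Grade 3 or worse pneumonitis and nephritis.

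**4. Recovery window.** 6 × 7 = 42 days; 12 × 7 = 84 days.

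- If the 6 weeks run from last dose, recovery on days 43 to 84 meets Table 4 only, a span of 42 days.
- If they run from onset or hold, assume onset before the next infusion. Infusions are every 21 days, each with a 3-day tolerance, so at most 21 + 3 + 3 = 27 days apart. The window then ends by day 27 + 42 = 69. Recovery on days 70 to 84 still meets Table 4 only, a span of 15 days.

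**5. Search for a precedence rule.**

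- Section 5.3.2.2 routes modification to the drug-specific guidelines.
- Section 5.3.2.2.1 makes withholding under Table 4 mandatory.
- Section 5.8 cites Section 5.3.2 for unacceptable toxicity.
- Table 7 in Section 7.2.4 requires advance sponsor approval, under the dose modification guidelines, for rechallenge after a serious event that the drug may have caused.

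All four lean towards Table 4. None mentions the Section 5.3.1 paragraph. Section 5.6.1 points to Section 5.2.1 for dose modification, but that section gives the radiation dose.

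**The case against.** The strongest reply is that the protocol, read as a whole, already protects the patient. Section 5.3.1 only permits resumption, whereas Tables 4 and 5 order a stop. Table 4's colitis entry is itself a condition for restarting and not a duty to restart. Following the stricter text therefore breaches neither, in every row. Life-threatening events are serious by definition (Section 7.2.3.1), so re-dosing after one needs the sponsor's prior approval. On the 6 weeks, Section 5.3.1 does not say what follows if they are exceeded, so Table 4 can fill the gap.

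Much of this stands, and it lowers the chance of a wrong re-dose. It does not remove the inconsistency. The protocol never says that the stricter text prevails. A reader can fairly take the DLT paragraph as the special rule for DLTs. For Grade 3 colitis and hypothyroidism, choosing the stricter text withholds treatment that Table 4 allows. The approval requirement covers serious events, or re-exposure that poses additional significant risk; a Grade 3 infusion reaction meeting neither condition is not caught.

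Three stronger readings are tempting but not supported:

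- **DLT counts or the MTD change.** A patient re-dosed after a DLT already counts. DLTs are counted by patient (Section 5.3.1), and a patient with a DLT is evaluable whatever is given later (Section 5.9).
- **Patients without a DLT become inevaluable.** One held infusion out of four (Days 1, 22, 43 and 64) gives 3/4 = 75%, below the 85% in Section 5.9. This assumes that the evaluation period contains all four infusions and that a held dose still counts as prescribed. The documents settle neither.
- **Sections 5.3 and 5.8 set contradictory treatment durations.** The limit of 12 months or 18 infusions sits under the maintenance phase. Counted from Day 43 it gives 2 + 18 = 20 infusions, which matches the flow chart (5 cycles × 4 = 20) and the count of 20 in Section 5.8. Section 5.8 can also be read as an outer limit on participation. The wording merits alignment, but a contradiction is not shown.

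**Conclusion.** The inconsistency is real and lies in the safety instructions. There are five mismatches: Section 5.3.1 is stricter or shorter on three and looser on two. The colitis bar and the two looser rules apply only to DLTs, so to roughly the first 12 to 13 weeks. The recovery window and the hypothyroidism hold apply to any related Grade 3 or 4 event. The gap in recovery time is 42 against 84 days, with 15 to 42 days of recovery times treated differently depending on the undefined start point. That range treats 6 weeks as a limit, which Section 5.3.1 implies but does not state.

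The effect is on patient safety and on consistent recording of pembrolizumab discontinuation and exposure. Sample size and planned analyses are untouched. How often these events will occur cannot be estimated from the documents.

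**What to change.** Replace the hold/resume paragraph in Section 5.3.1 with a statement that Table 4, together with Table 5 for infusion reactions, governs every pembrolizumab hold, restart and discontinuation, including after a DLT. If the sponsor wants the Grade 3 colitis stop or the 6-week limit, move it into Table 4 with a defined start point and a stated consequence when the limit is passed. Correct the Section 5.6.1 cross-reference so that it points to Section 5.3.2.2.1.

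The cost is one paragraph and one cross-reference, plus a sponsor decision on the two stricter limits. The DLT definition, sample size and analysis stay as they are. As a side note, the treatment-completion wording in Sections 5.3 and 5.8 should be made consistent in the same amendment.
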